- Hepatitis A virus (HAV) screening is not necessary, screenings required above is for identification of chronic diseases.

I 10. Screening hematology, clinical chemistries, coagulation, and urinalysis are not clinically significant, as assessed by the Investigator, and meet the following criteria:

- A) Platelets, total white blood cell (WBC) count, and absolute neutrophil count within normal limits
- B) Hemoglobin (Hb) ≥ 11 g/Dl
- C) Total and direct bilirubin <1.5 x upper limit of normal (ULN), unless elevated bilirubin is associated with a known benign condition (eg, Gilbert's syndrome)

- D) Alanine aminotransferase (ALT) <1.5 x ULN
- E) Aspartate aminotransferase (AST) <1.5 x ULN
- F) Alkaline phosphatase (ALP) <1.5 x ULN
- G) Gamma-glutamyl transferase (GGT) <1.5 x ULN

Note: At the discretion of the Investigator, screening laboratory testing may be repeated once to confirm out-of-range (exclusionary) results.

- I 11. Agree to report any new prescription medication, dose adjustment to existing medication, over-the-counter medication, or herbal supplement to the Investigator.
- I 12. Able to understand all study procedures in the informed consent form (ICF) and willing to comply with all aspects of the protocol.

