3.3.1.1 Individual treatment stopping criteria

Any Grade 2 AE (except for renal function parameters related to the underlying disease process including eGFR, creatinine, BUN, and urinalysis) not resolved prior to the administering the next dose and deemed by the Investigator to be at least "possibly related" to study drug would result in a pausing of dosing (eg, dose not given) until the AE improves to \leq Grade 1. Injection site reactions will be graded according to [Table 6](#). Any Grade 2 (except erythema/redness) or Grade 3 ISRs which had not resolved or reached Grade 1 ("Mild", eg, limited tenderness, and/or induration, except erythema/redness) prior to the next dose, would result in a pausing of dosing. The continuation of dosing and dose level would be decided upon review between the Investigator and the Genzyme Corporation Study Medical Manager. For further details in dose reduction, see [Section 4.5](#).

Occurrence of any Grade 3 (Severe) or higher AE (except for ISRs and renal function parameters related to the underlying disease process including eGFR, creatinine, BUN, and urinalysis) will result in the cessation of dosing of the subject, unless it can be shown that the event was unrelated to participation in the clinical trial. The DMC will review the circumstances of the AE with the Sponsor and unblind the subject, as appropriate, to evaluate potential relatedness to study drug and will make a recommendation regarding the further dosing of the subject to the Sponsor. After deliberations, DMC will provide guidance to the Sponsor who will implement recommendations and communicate to the site.

With regard to AEs, study drug should be discontinued for subjects who experience any of the following:

- Grade 3 thrombocytopenia (platelet count from $<50\,000$ to $25\,000/\text{microL}$) will trigger cessation of dosing for the subject.
- ALT or AST $>5 \times$ ULN, or ALT or AST $>3 \times$ ULN in association with total bilirubin $>2 \times$ ULN.
- An unintended weight loss of $\geq 20\%$ from baseline.

- $\geq 50\%$ decline for eGFR from the last measurement or confirmed ESRD (eGFR ≤ 15 mL/min/1.73 m² or dialysis or renal transplantation is needed).

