Alkaline phosphatase	1.25 to <2.5 x ULN	2.5 to <5.0 x ULN	5.0 to <10.0 x ULN	\geq 10.0 x ULN
eGFR ^b	NA	10 to <30% decrease from participant's baseline	30 to <50% decrease from participant's baseline	\geq 50% decrease from participant's baseline or dialysis needed

ALT: alanine aminotransferase; AST: aspartate aminotransferase; eGFR: estimated glomerular filtration rate; NA: not applicable; ULN: upper limit of normal

Grading criteria are based on the DAIDS grading system (1). All deaths related to an AE are to be classified as Grade 5.

a For management of elevated aminotransferases, please refer to protocol Section 10.3.2.

b If there is any eGFR grade 2 (toxicity grade 2 or intensity moderate) events retain in the clinical database as AESI due to old AESI grading system, they will not be considered as AESI at the analysis level.

For criteria of direct bilirubin Grades 3 and 4 mentioned in Table 6, they are further specified as below:

- Grade 3:
 - Direct bilirubin > ULN + mild to moderate (intensity) Fatigue or/and Nausea or/and Pruritus or/and Oedema peripheral or/and Ascites + Grade 3 (toxicity) Alanine aminotransferase increased or/and Aspartate aminotransferase increased, or
 - Direct bilirubin > ULN + mild to moderate (intensity) Jaundice, or
 - Direct bilirubin > ULN + mild to moderate (intensity) Haemorrhage, or
 - Direct bilirubin > ULN + Grade 3 (toxicity grade) Alanine aminotransferase increased or/and Aspartate aminotransferase increased.
- Grade 4:
 - Direct bilirubin > ULN + severe (intensity) Fatigue or/and Nausea or/and Pruritus or/and Oedema peripheral or/and Ascites + \geq Grade 4 (toxicity) Alanine aminotransferase increased or/and Aspartate aminotransferase increased, or
 - Direct bilirubin > ULN + severe (intensity) Jaundice, or
 - Direct bilirubin > ULN + severe (intensity) Haemorrhage, or
 - Direct bilirubin > ULN + Hepatic encephalopathy, or
 - Direct bilirubin > ULN + \geq Grade 4 (toxicity) Alanine aminotransferase increased or/and Aspartate aminotransferase increased.

When the ULN for direct bilirubin is not available, 7 umol/L will be used.

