To notice that the AEs must happen within 7 days before or concomitant with the event of direct bilirubin >ULN during the same treatment emergent period. For example, if the event of direct bilirubin >ULN happened on October 1, 2021 00:00AM during the placebo-controlled treatment period, only if the mild Haemorrhage started between September 24, 2021 00:00AM (exclusion) to October 1, 2021 00:00AM (inclusion) during the placebo-controlled treatment period, it will be considered as meeting the criteria of Grade 3 direct bilirubin during the placebo-controlled treatment period.

The **primary focus** of adverse event reporting will be on double blind period in placebo-controlled treatment-emergent events on the safety population unless otherwise specified. Key adverse events will also be summarized for the lademirsen treated population in lademirsen treatment period.

Generalities

If an adverse event date/time of onset (occurrence, worsening, or becoming serious) is incomplete, an imputation algorithm will be used to classify the adverse event as pre-treatment and treatment-emergent periods. The algorithm for imputing date/time of onset will be conservative and will classify an adverse event as treatment emergent unless there is definitive information to determine it is not on treatment emergent periods. Details on classification of adverse events with missing or partial onset dates are provided in [Section 5.3](#).

Adverse event incidence tables will present by SOC, and PT, sorted by internationally agreed order of primary SOC and by decreasing incidence of PTs within each SOC, the number (n) and percentage (%) of participants experiencing an adverse event. Multiple occurrences of the same event in the same participant will be counted only once in the tables within a treatment phase. The denominator for computation of percentages is the defined population (eg, safety population, lademirsen treated population) within each treatment group. Sorting will be based on results of the lademirsen group if the analysis is on DB TE period or the overall group if the analysis is on lademirsen TE period.

Analysis of all treatment-emergent adverse events

- Overview of treatment-emergent adverse events, summarizing number (%) of participants with any
 - Treatment-emergent adverse event,
 - Serious treatment-emergent adverse event,
 - Treatment-emergent adverse event leading to death,
 - Treatment-emergent adverse event leading to dose reduction, and

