4.7.3 Laboratory variables, vital signs and electrocardiograms (ECGs)

The summary statistics (including number, mean, median, Q1, Q3, standard deviation, minimum and maximum) of all laboratory variables (central laboratory values and changes from baseline) based on availability will be calculated for each visit or study assessments (baseline, each post-baseline time point, last on-treatment during placebo-controlled treatment period and lademirsen treatment period respectively, and worst on-treatment value during placebo-controlled treatment period and lademirsen treatment period respectively) by treatment group during the overall study period.

For selected laboratory parameters (eg, platelet, creatinine, proteinuria [protein/creatinine ratio], albumin/creatinine ratio, eGFR, and selected parameters in liver function), individual participant plots will be prepared for the observed value overtime during overall study period. For selected kidney parameters (eg, cystatin C, and blood urea nitrogen), mean (+/-SE) plots will be prepared for the observed value over time during the double-blind period, and also by screening eGFR stratification factor.

The incidence of PCSAs at any time during the placebo-control treatment-emergent period and lademirsen treatment-emergent period, respectively, will be summarized by biological function and treatment group whatever the baseline level is.

For PCSA analyses, the laboratory measurements obtained at either scheduled or unscheduled visits should be used; and, both the centralized and local test results should be used, as long as their available dates/time is different from each other's. Centralized data will be used

preferentially to the local measures in the PCSA analyses when measurements are performed on the same date and at the same time for a given laboratory test.

Listing of PCSAs during the overall study period will be provided.

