5.7 APPENDIX 7 FACIT-F QUESTIONNAIRE AND SCORING TRANSFORMATION

5.8 APPENDIX 8 POTENTIALLY CLINICALLY SIGNIFICANT ABNORMALITIES CRITERIA

Potentially clinically significant abnormalities criteria

CRITERIA for POTENTIALLY CLINICALLY SIGNIFICANT ABNORMALITIES for Phase 2/3 studies (oncology excepted) (From BTD-009536 - 21-MAY-2014, except for parameters eGFR and CLcr)		
Parameter	PCSA	Comments
Clinical Chemistry		
ALT	By distribution analysis:	Enzymes activities must be expressed in ULN, not in IU/L.
	>3 ULN	Concept paper on DILI - FDA draft Guidance Oct 2007.
	>5 ULN	Internal DILI WG Oct 2008.
	>10 ULN	Categories are cumulative.
	>20 ULN	First row is mandatory. Rows following one mentioning zero can be deleted.
AST	By distribution analysis:	Enzymes activities must be expressed in ULN, not in IU/L.
	>3 ULN	Concept paper on DILI – FDA draft Guidance Oct 2007.
	>5 ULN	Internal DILI WG Oct 2008.
	>10 ULN	Categories are cumulative.
	>20 ULN	First row is mandatory. Rows following one mentioning zero can be deleted.
Alkaline Phosphatase	>1.5 ULN	Enzymes activities must be expressed in ULN, not in IU/L. Concept paper on DILI – FDA draft Guidance Oct 2007. Internal DILI WG Oct 2008.
	>1.5 ULN	Must be expressed in ULN, not in µmol/L or mg/L. Categories are cumulative.
Total Bilirubin	>2 ULN	Concept paper on DILI – FDA draft Guidance Oct 2007. Internal DILI WG Oct 2008.
	>35% Total Bilirubin (TBILI) and TBILI >1.5 ULN	Conjugated bilirubin based on a case-by-case basis.
Conjugated (direct) Bilirubin		Concept paper on DILI - FDA draft Guidance Oct 2007.
ALT and Total Bilirubin	ALT >3 ULN and TBILI >2 ULN	Internal DILI WG Oct 2008.
		To be counted within a same treatment phase, whatever the interval between measurement.

CRITERIA for POTENTIALLY CLINICALLY SIGNIFICANT ABNORMALITIES
for Phase 2/3 studies (oncology excepted)
(From BTD-009536 - 21-MAY-2014, except for parameters eGFR and CLcr)

Parameter	PCSA	Comments

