Safety population for analysis during the placebo-controlled period; Lademirsen population for analysis during the lademirsen treatment period	To assess the safety and tolerability of lademirsen in participants with Alport syndrome. ^c	Incidence and severity of treatment-emergent adverse events (TEAEs) and serious adverse events (SAEs) during the placebo-controlled treatment period and lademirsen treatment period, respectively Number of participants with PCSA in clinical laboratory parameters during the placebo-controlled treatment period Number of participants with PCSA in vital signs during the placebo-controlled treatment period Number of participants with PCSA in 12-lead electrocardiogram (ECG) during the placebo-controlled treatment period

Population ^a	Objectives	Endpoints
PK population	To assess plasma pharmacokinetic (PK) parameters. Concentration at 4 hours post dosing (approximate C _{max} for the parent compound) for lademirsen, its active major metabolite (RG0005), and the sum of lademirsen and RG0005 (SUM) following administration of lademirsen. C _{trough} will be assessed in terms of SUM only.	Plasma concentrations of lademirsen, RG0005, and SUM (lademirsen + RG0005) in C _{max} samples and SUM only in C _{trough} samples during the placebo-controlled treatment period
ADA population	To assess potential formation of anti-drug antibodies (ADAs) following administration of lademirsen.	Incidence and titer of ADAs during the placebo-controlled treatment period Association of AEs with ADAs during the placebo-controlled treatment period
ITT population	To assess the pharmacodynamic effect of lademirsen on changes in kidney injury and function biomarkers.	Change in kidney injury and function biomarkers from baseline at Weeks 24 and 48 during the placebo-controlled treatment period: 
 In blood: blood urea nitrogen (BUN); In urine^b: protein/creatinine ratio, albumin/creatinine ratio, and epidermal growth factor (EGF)/creatinine ratio; In both blood and urine^b: creatinine, Cystatin C, transforming growth factor-β (TGFβ), and neutrophil gelatinase-associated lipocalin (NGAL).
Exploratory		

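### The combined liver abnormality row in SAP Appendix 8 uses ALT only, so a participant who meets the protocol's AST-plus-bilirubin discontinuation criterion can be missing from it

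*SAP*

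**What the plan says.** SAP Section 5.8 (Appendix 8) lists ALT and AST separately at more than 3, 5, 10 and 20 x ULN, and total bilirubin at more than 1.5 and 2 x ULN. One row combines an enzyme with total bilirubin, "ALT >3 ULN and TBILI >2 ULN", with the comment "To be counted within a same treatment phase, whatever the interval between measurement". No row combines AST with total bilirubin.

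SAP Section 4.7.3 summarises "The incidence of PCSAs at any time during the placebo-control treatment-emergent period and lademirsen treatment-emergent period, respectively". The SAP addendum (Section 3, Table 1), which governs the final analysis after early termination, gives the laboratory safety endpoint as "Number of participants with PCSA in clinical laboratory parameters during the placebo-controlled treatment period". It does not change the criterion.

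Protocol Section 3.3.1.1 and the synopsis discontinue study drug for ALT or AST above 5 x ULN, or for ALT or AST above 3 x ULN "in association with total bilirubin" above 2 x ULN.

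SAP Section 4.7.2 has another composite liver rule, for direct bilirubin Grades 3 and 4. One of its limbs is direct bilirubin above ULN with "Grade 3 (toxicity grade) Alanine aminotransferase increased or/and Aspartate aminotransferase increased". Other limbs use jaundice, haemorrhage or, for Grade 4, hepatic encephalopathy, with no enzyme threshold. Its timing rule is that "the AEs must happen within 7 days before or concomitant with the event of direct bilirubin" above ULN.

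**The concern.** The combined row is the only tabulated count that joins an aminotransferase with total bilirubin at the protocol's 3 x and 2 x ULN limits. Because it names ALT alone, it can give zero for a participant who meets the criterion that the protocol itself uses to stop drug.

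Protocol Section 1.3.1 names hepatotoxicity as an important potential risk, and the addendum makes PCSA counts the laboratory safety endpoint. A reader comparing arms on that row would take it as the count of participants with the combined finding and could undercount them. The SAP's direct-bilirubin rule accepts either enzyme, so leaving AST out of this row is not consistent practice within the SAP.

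**Working it through.** No figure in the plan needs reproducing. The check applies the rules to constructed profiles and then looks for another output that would show the combination.

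**Inputs**
- SAP row (Section 5.8): highest ALT > 3 x ULN and highest total bilirubin > 2 x ULN, anywhere in the same treatment phase.
- Protocol criterion (Section 3.3.1.1): ALT or AST > 5 x ULN; or ALT or AST > 3 x ULN with total bilirubin > 2 x ULN. It is read here as the same sample, because the protocol gives no window.
- Chemistry schedule (Protocol Table 1; SAP Section 5.3 for eGFR): Week 2, Week 4, then every 4 weeks.

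**Profiles (multiples of ULN)**

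| Profile | Protocol criterion | SAP combined row | Row with ALT or AST, any interval | ALT or AST, same sample |
|---|---|---|---|---|
| 1. ALT 2.8, AST 3.5, bilirubin 2.2, one visit | met | not counted | counted | counted |
| 2. ALT 3.2, AST 4.5, bilirubin 2.2, one visit | met | counted | counted | counted |
| 3. ALT 3.2 at Week 2 with normal bilirubin; bilirubin 2.1 at Week 48 with normal ALT | not met in one sample | counted | counted | not counted |

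Profile 1 is the gap. Profile 2 shows its limit: once ALT also passes 3 x ULN at any time in the phase, the participant is counted. Profile 3 shows how far apart the two findings may lie: 48 − 2 = 46 weeks between scheduled post-baseline samples in the 48-week double-blind period.

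**Would another output show Profile 1 as a combination?**
- Single-parameter PCSA rows: AST > 3 x ULN and bilirubin > 2 x ULN are each ticked, but in separate rows.
- Grading table (SAP Table 6): AST 3.5 lies in 2.5 to < 5.0 and bilirubin 2.2 lies in 1.6 to < 2.6. Each is Grade 2 and graded on its own.
- Direct-bilirubin rule: the enzyme limb needs Grade 3, which starts at 5.0 x ULN, and AST is 3.5. The rule is met only if direct bilirubin is above ULN with a listed clinical event, such as jaundice or haemorrhage, that needs no enzyme threshold.

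The combination is therefore untabulated when AST is above 3 and below 5 x ULN, bilirubin is above 2 x ULN, ALT stays at or below 3 x ULN throughout the phase, and no such clinical event accompanies a raised direct bilirubin.

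**Size of one case**

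SAP Section 1.1 gives 43 Stage 1 participants randomised 2:1. 43 × 2/3 = 28.7, about 29; 43 × 1/3 = 14.3, about 14. One participant is 1/29 = 3.4% of the lademirsen arm or 1/14 = 7.1% of the placebo arm.

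**The case against.** The PCSA table is a sponsor-standard list, and Protocol Section 7.2.4 defines PCSAs by sponsor thresholds based on literature review. Nothing requires them to reproduce the individual stopping rule. This stands: the two are different instruments, and the mismatch is not a breach of the protocol.

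The case is also visible elsewhere. The Grade 2 AST and bilirubin values are AESIs under Protocol Section 6.2.2. SAP Version 2.0 plans AESI summaries, a PCSA listing and a table of adverse events leading to discontinuation. With 43 participants, someone reading the listings would probably find it. This stands too, and it keeps the point small. It does not provide a count of the combination.

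A reader might infer that counting at any interval is itself an error, because Profile 3 joins findings 46 weeks apart. The documents do not support that. The comment in the row is explicit and reads as a deliberately inclusive screen. The protocol sets no window for the association, and neither document gives one for pairing these two liver tests. The rule also narrows the AST gap, since a later ALT rise brings the participant in.

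A reader might also infer a fault from inclusion criterion I10 C, which admits raised bilirubin "unless elevated bilirubin is associated with a known benign condition", because one transient ALT rise could then make a combined case. The protocol's stopping criterion has no exemption for such participants either, so this does not separate the SAP from the protocol. No document says that any such participant enrolled.

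**Conclusion.** The point holds for the enzyme term. A participant can meet the protocol's AST-plus-bilirubin criterion and score zero in the SAP's combined row, provided ALT never exceeds 3 x ULN in that phase. It does not follow that the case goes unreported, that the any-interval rule is wrong, or that this is the SAP's only marker of serious liver injury. The SAP also has higher single-enzyme thresholds and the direct-bilirubin rule.

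The 3.4 and 7.1 percentage points assume a 29/14 split, which follows from 2:1 allocation of 43; the documents do not report actual arm sizes. They are the weight of a single case, not an expected rate. The table is descriptive, and no test, efficacy analysis or clinical threshold depends on it. This is a low-cost improvement to a safety table.

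**What to change.** In SAP Appendix 8, change the combined tabulation row to (ALT or AST) > 3 ULN and TBILI > 2 ULN, so that it uses the same enzyme terms as the protocol criterion. Keep the count at any interval within a treatment phase as the inclusive screen. Carry the change into the addendum's laboratory PCSA output.

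Optionally, add a descriptive line for participants with both elevations in the same sample, and flag those with baseline bilirubin above ULN. These help the reader interpret the count and do not correct an error.

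The cost is one table row and minor programming. The downside is that AST can rise from muscle, so a few added cases may need narrative review.

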1 BACKGROUND

The SAP Version 2.0 (dated 04 May 2022) was developed based on Amended Protocol 13 (dated 05 May 2022). Both documents were approved at Sanofi internally before the first DBL (22 Apr 2022) for the purpose of the first interim analysis for futility. This Amended Protocol 13 is a substantial amendment by amending the Phase 2 study design from Amended Protocol 11 (and Amended Protocol 12, for France only) to a Phase 2b, 2-stage seamless design with the following major modifications:

- Stage 1 consisted of study design from original Phase 2 study as described in Amended Protocols 11 and 12. The first interim futility analysis planned in Amended Protocols 11 and 12 was also kept in the Amended Protocol 13 with updates in statistical analysis method.
- Stage 2 consisted of newly enrolled participants for 96 weeks double blind treatment period.

The Amended Protocol 13 was approved at Sanofi internally. However due to study termination after first interim analysis for futility, this protocol was withdrawn from health authority (HA) submission. The latest protocol version approved globally by HA was Amended Protocol 11 and Amended Protocol 12, for France only.

2 PURPOSE OF ADDENDUM

The purpose of developing this study analysis plan (SAP) Version 2.0 addendum is to:

- Describe the major changes in study design for the final database lock (DBL) which are not reflected in SAP Version 2.0, and
- Explain the impact of following the internally approved Amended Protocol 13 on statistical analysis.

3 DESCRIPTION OF CHANGES

This SAP Version 2.0 addendum is developed prior to the final DBL (planned for 04 Nov 2022) by following decision to not start Stage 2 enrollment and study termination based on futility analysis result. As the study was terminated early, prior to all Stage 1 participants' completion of the double blind (DB) period of the study, and no Stage 2 participants are enrolled, only key endpoints are planned to be analyzed and the time frame of analysis is reduced to Week 48 for efficacy and most of the safety analyses. Only for limited key safety analyses, the analyses will include up to 96 weeks of the lademirsen treated period. No multiplicity adjustment will be performed. The modified objectives and endpoints are specified in Table 1, which is aligned with the endpoints defined in Amended Protocols 11, 12 and 13. However, there is no major change of the analysis plan regarding the statistical method. For efficacy analyses, as no Stage 2 participants are enrolled, all statistical method will only include Stage 1 participants, and the covariates only pertinent to Stage 2 participants will be removed.

Table 1 - Objectives and endpoints for final analysis (modified after the decision of study termination)

Population ^a	Objectives	Endpoints
Primary		
Primary population	To assess the efficacy of lademirsen in reducing the rate of decline in kidney function as compared to placebo in participants at risk for rapidly progressive Alport syndrome	Annualized rate of change in estimated glomerular filtration rate (eGFR) during the placebo-controlled treatment period
Secondary		
ITT population	To assess the efficacy of lademirsen in reducing the absolute decline in kidney function at Week 48	Absolute and percentage change in eGFR values from baseline at Week 24 and 48 Proportion of participants with a reduction from baseline in eGFR of <10%, <20%, <30%, or <40% at Week 24 and 48
ITT population	To assess the efficacy of lademirsen in delaying time to reach the ESRD	Number and proportion of participants who reach ESRD as defined by an eGFR ≤ 15 mL/min/1.73 m ² or initiation of hemodialysis or renal transplantation (composite endpoint) during the placebo-controlled treatment period
Safety population for analysis during the placebo-controlled period; Lademirsen population for analysis during the lademirsen treatment period	To assess the safety and tolerability of lademirsen in participants with Alport syndrome. ^c	Incidence and severity of treatment-emergent adverse events (TEAEs) and serious adverse events (SAEs) during the placebo-controlled treatment period and lademirsen treatment period, respectively Number of participants with PCSA in clinical laboratory parameters during the placebo-controlled treatment period Number of participants with PCSA in vital signs during the placebo-controlled treatment period Number of participants with PCSA in 12-lead electrocardiogram (ECG) during the placebo-controlled treatment period

Population ^a	Objectives	Endpoints
PK population	To assess plasma pharmacokinetic (PK) parameters. Concentration at 4 hours post dosing (approximate C _{max} for the parent compound) for lademirsen, its active major metabolite (RG0005), and the sum of lademirsen and RG0005 (SUM) following administration of lademirsen. C _{trough} will be assessed in terms of SUM only.	Plasma concentrations of lademirsen, RG0005, and SUM (lademirsen + RG0005) in C _{max} samples and SUM only in C _{trough} samples during the placebo-controlled treatment period
ADA population	To assess potential formation of anti-drug antibodies (ADAs) following administration of lademirsen.	Incidence and titer of ADAs during the placebo-controlled treatment period Association of AEs with ADAs during the placebo-controlled treatment period
ITT population	To assess the pharmacodynamic effect of lademirsen on changes in kidney injury and function biomarkers.	Change in kidney injury and function biomarkers from baseline at Weeks 24 and 48 during the placebo-controlled treatment period: 
 In blood: blood urea nitrogen (BUN); In urine^b: protein/creatinine ratio, albumin/creatinine ratio, and epidermal growth factor (EGF)/creatinine ratio; In both blood and urine^b: creatinine, Cystatin C, transforming growth factor-β (TGFβ), and neutrophil gelatinase-associated lipocalin (NGAL).
Exploratory		
ITT population	To assess the effect of lademirsen on urine and blood biomarkers in Alport Syndrome participants.	Changes in exploratory biomarkers from baseline at Weeks 24 and 48 during the placebo-controlled treatment period: 
 In both blood and urine^b: β-2 microglobulin and connective tissue growth factor (CTGF) In urine only^b: kidney injury molecule-1 (KIM-1)/creatinine ratio and calbindin-D28k/creatinine ratio
ITT population	To assess the efficacy of lademirsen in reducing the decline in hearing sensitivities at Week 48.	Change from baseline at Week 48 in degrees of hearing level recorded in both ears measured by a pure tone audiometry in the placebo controlled treatment period

^a The definition of population is in [Table 2](#).

^b Urine biomarkers will be standardized by creatinine before analysis. If the urine parameter is collected through 24-hour urine, then the standardized value will be calculated by the original value divided by 24-hour urine creatinine; else if the urine parameter is collected through instant urine, then the standardized value will be calculated by divided by instant urine creatinine.

^c This is one of the primary objectives for Amended Protocol 11 and 12, and secondary objective for Amended Protocol 13.

Table 2 - Populations for analyses

Population	Description
Randomized population	All randomized participants. Participants will be analyzed according to the study intervention allocated by randomization.
ITT population	All randomized participants. Participants will be analyzed according to the study intervention allocated by randomization.
Compliant ITT population	All randomized participants who received $\geq 80\%$ planned IMP during the double-blinded, placebo-controlled treatment period Participants will be analyzed according to the intervention allocated by randomization.
Primary population	All randomized participants who completed the double-blinded period (the first 48 weeks) or discontinued double-blinded period early. Participants will be analyzed according to the study intervention allocated by randomization.
Compliant primary population	All randomized participants who completed the double-blinded period (the first 48 weeks) or discontinued double-blinded period early, and received $\geq 80\%$ planned study intervention during the double-blinded treatment period Participants will be analyzed according to the study intervention allocated by randomization.
Safety population	All randomized participants who received at least 1 or partial dose of study intervention. Participants will be analyzed according to the study intervention they actually received.
PK population	All treated participants who received at least one dose of the lademirsen in DB period and had at least one post dose PK sample collected in DB period for determination of lademirsen concentrations.
ADA population	All randomized participants who received at least 1 of study intervention (safety population) who had at least one post-baseline ADA sample collected in placebo-controlled, double blind period.
Lademirsen treated population	Randomized population who actually received at least 1 or partial dose of lademirsen during the study.

